10. STATISTICAL CONSIDERATIONS

Full details of all statistical analyses will be pre-specified in a statistical analysis plan which will be written and approved prior to release of any unblinded data to the senior and trial statisticians.

The trial statistician and senior trial statistician will be unblinded for the purposes of producing and reviewing reports to the Data Monitoring Committee (DMC). Unblinded reports will be kept confidential and will only be viewed by the DMC members and the senior and trial statistician. The statistical analysis plan will be written and approved by the senior and trial statistician prior to any access to unblinded outcome data. A statistical methodology advisor will also be involved in the trial

and will remain blinded to outcome data until data lock for the primary analysis. Should any amendments to the statistical analysis plan be required after the senior and trial statisticians have accessed unblinded outcome data these can be reviewed and approved by the blinded statistical methodology advisor.

10.1. Analysis Populations

The following analysis populations are defined for the purpose of analysis:

Analysis Population	Description			
Intention-to-treat (ITT)	Includes all randomised participants, analysed according to			
	randomised treatment allocation.			
Modified intention-to-treat	Includes all randomised participants, continuing to meet the			
	eligibility criteria at the time of intervention, analysed according to			
	randomised treatment allocation.			
Per-protocol	Includes all randomised participants receiving their allocated			
	intervention and continuing to meet the eligibility criteria at the time			
	of intervention, analysed according to randomised treatment			
	allocation.			
As-treated	Includes all randomised participants receiving one of the trial			
	interventions and continuing to meet the eligibility criteria at the			
	time of intervention, analysed according to treatment received.			
Safety	Includes all randomised participants receiving a trial intervention,			
	analysed according to the intervention received.			

For the main analysis of efficacy outcomes, participants will be analysed according to their randomised treatment allocation; whereas safety data and post-operative complications will be reported and analysed according to the intervention they actually received.

10.2. Sample Size Calculations

The primary outcome is the change in I-PSS total score between baseline and 12 months. The trial is powered to test the non-inferiority (NI) of each experimental arm to the TURP arm in terms of I-PSS. The three null hypotheses to be tested are:

- The mean difference in 12-month I-PSS total score (adjusted for baseline) between PUL and TURP is > 3
- ii. The mean difference in 12-month I-PSS total score (adjusted for baseline) between Rezum and TURP is > 3
- iii. The mean difference in 12-month I-PSS total score (adjusted for baseline) between iTIND and TURP is > 3

To test each hypothesis, participants will be pooled across the following randomisation schemes:

i. TURP vs PUL ii. TURP vs Rezum		iii. TURP vs iTIND
TURP: PUL: Rezum: iTIND	TURP: PUL: Rezum: iTIND	TURP: PUL: Rezum: iTIND
TURP: PUL: Rezum	TURP: PUL: Rezum	TURP: PUL: iTIND
TURP: PUL: iTIND	TURP: Rezum: iTIND	TURP: Rezum: iTIND
TURP: PUL	TURP: Rezum	TURP: iTIND

In data from the UNBLOCS trial (NIHR HTA 12-35-15) [33] the standard deviation (SD) of the I-PSS score at 12-months follow-up was 6.3 (based on the non-catheterised participants with complete data).

A non-inferiority margin of three points is used. This represents the minimally clinically important difference (MCID) for the outcome. [4,46,47] The non-inferiority hypothesis is equivalent to ruling out TURP providing an improvement of the MCID or greater against a minimally invasive treatment.

Assuming a minimally invasive arm has the same mean I-PSS as TURP, standard non-inferiority sample size formula suggests we would require 12-month information on 100 participants per intervention for each comparison for 90% power to conclude non-inferiority at a one-sided type I error rate of 0.0195 (nQuery). This p-value threshold yields a maximum chance of falsely concluding non-inferiority of 5% assuming a Dunnett correction.

We have inflated this sample size to account for a 25% attrition rate, which was seen in UNBLOCS for patient-reported outcomes. This gives a sample size of 134 participants per intervention for each comparison. Since we are adjusting for baseline I-PSS, we would expect power to be higher than 90%.

The minimum required sample size will therefore be 536 participants, however due to the nature of the personalised randomised design, not all participants will contribute to each analysis, and it is likely that over-recruitment will be required to obtain a sufficient number of participants receiving each intervention for each comparison. The number of participants recruited into each randomisation scheme and the number of participants available for each analysis will be closely monitored by the Trial Management Group. If it becomes apparent that low numbers of participants are being recruited to one intervention, such that the power likely to be achieved for comparisons involving that arm are substantially reduced, the utility of continuing to recruit to randomisation schemes containing that intervention will be evaluated and discussed with the DMC, TSC and Funder. In the event it is not feasible to recruit a sufficient number of participants to TURP we will consider utilising historical control data from previously conducted randomised controlled trials.

10.3. Statistical Analyses

10.3.1. Analysis of the Primary Outcome Measure

Main analysis methods

The main primary objective is to estimate the mean difference in the change in the I-PSS symptom score from baseline to 12 months in men requiring surgery for BOO treated with each MIT compared to TURP assuming all eligible patients would adhere to their randomised treatment allocation.

The main primary estimand is described by the following attributes:

Estimand attribute	Description		
Population	Patients offered surgery for BOO and meeting the PREMISE eligibility		
	criteria		
Treatment conditions	Intervention via PUL, iTIND, Rezum (MITS) vs TURP (Control)		
Outcome measure	Change in I-PSS score from baseline to 12-month follow-up		
Strategies used to handle	Becoming ineligible between randomisation and intervention -		
intercurrent events	principal strata ¹		
	Not undergoing randomised treatment – hypothetical ²		
Population-level summary	Mean difference in I-PSS score at 12 months (adjusted for baseline)		
measure	between each MITS and TURP		

¹The principal strata strategy targets the treatment effect within the subgroup of patients who would not have the intercurrent event, regardless of allocated treatment group

For the pairwise comparison of each MIT to TURP data will be pooled across randomisation schemes as shown in Section 10.2.

If, within each comparison, the proportion of eligible participants not undergoing their allocated treatment is >5% in either randomised treatment group inverse probability weighting (IPW) will be used to estimate the average causal effect of each MIT compared to TURP in the hypothetical setting where all eligible participants adhere to their allocated treatment. This will be implemented in two stages. In the first stage, a logistic regression model will be fitted separately to each randomised treatment group with adherence to assigned treatment as the outcome (dependent variable) and prespecified baseline measures as covariates (to be identified following a review of literature and expert opinion and agreed prior to data lock for the main analysis). The modified ITT population will be used, with all participants continuing to meet the eligibility criteria included. These models will be used to calculate weights (the inverse of participant specific predicted probabilities of adhering to allocated treatment) to be used in the main analysis model (second stage).

The main analysis will be carried out in the per-protocol population. A linear mixed-effects model (mixed model for repeated measures) will be fitted to the six- and twelve-month I-PSS total score data, with fixed effects for baseline I-PSS, randomisation scheme, and a treatment-by-time interaction term. Random effects for site (this will be the Hub where a Hub and Spoke model is used) and individual (nested within site) will be used. Where required, the model will be weighted using the weights calculated as described above.

The estimated difference between control and each experimental treatment at 12 months will be extracted from the model and reported with 95% confidence intervals. Adjusted 95% CI will also be provided as supplementary information. The one-sided p-value for non-inferiority (with margin three) will be calculated. The critical p-value threshold will be set as 0.0195 so that the maximum chance of incorrectly concluding an arm is non-inferior when they all are inferior is 5% (following the Dunnett procedure).

The experimental arms will be compared to one another for the primary outcome, although the trial is not powered for this comparison.

²The hypothetical strategy targets the treatment effect in the hypothetical setting where the intercurrent event did not occur

Sensitivity analyses

Where IPW methods are used for the main analysis the analysis will be repeated without the use of IPW methods.

Supplementary analyses

Analyses will be repeated in the as-treated, modified ITT and ITT populations. We will also estimate the Complier Average Causal Effect (CACE) using Instrumental Variable (IV) methods.

We will also repeat the main analysis but with participants pooled across all 11 randomisation schemes. Appropriate methods, e.g. weighting procedures, will be used to account for any differences in patient-level variables between arms.

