
Prostatic urethral lift: PUL is a minimally invasive treatment which does not excise or ablate tissue, and so avoids some adverse effects. PUL is also known as Urolift (trade name). PUL is intended for men with bothersome LUTS, where intervention is being considered, but TURP or equivalent is not

felt acceptable by the patient. Nearly all other less invasive procedures have involved a mechanism of action using thermal energy to effect tissue necrosis. Because tissue ablation relies on subsequent healing, recovery is often not achieved for several weeks, during which time substantial symptoms may be present. Some thermal ablation technologies are associated with sexual dysfunction (erectile dysfunction ≤3%, ejaculatory dysfunction 5%-15%).[24] PUL was developed to avoid delivery of energy. It was approved by the FDA in 2013, and by NICE in 2015. PUL involves placing non-absorbable sutures with a nitinol prostate capsular anchor and a stainless-steel urethral end piece to mechanically open up the anterior prostatic fossa and disobstruct the urethra.[25] Treatment can be administered in an outpatient setting under local anaesthesia. [26] Patient recovery is quick, with mild to moderate adverse events that typically resolve by two to four weeks.[27] Need for further treatment is relatively low (2.5-9%). [27,28] Patients with enlarged median lobes may also be treated with similar outcomes.[29] Recent data has also supported the use of PUL as a treatment for catheterised men. Despite the limited evidence base, PUL has become a widely disseminated treatment option for patients with LUTS worldwide.[28]

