4. TRIAL DESIGN

Multi-arm, multi-centre, open-label, non-inferiority, personalised randomised controlled trial with a six-month internal pilot with defined progression criteria. In total, a minimum of 536 participants will be recruited and followed up for three years post-intervention.

Patients who are willing to receive at least two of the four trial interventions can be randomised among treatments they are willing to receive. There are 11 possible randomisation schemes for patients to choose from. (See section 7.2.) Site staff will be counselled to retain equipoise between all four interventions and should not aim to influence the participants choice for the interventions they are willing to receive. To mitigate against surgeon influence the pattern of participant choice will be monitored across sites.

All sites will offer all interventions. In some sites this may be through the use of a Hub and Spoke model, which functions by allowing patients to access a variety of treatments within their locality but not necessarily in their originating hospital or trust. Where this is the case trial participants may receive their study intervention at another hospital or trust, referred to as a 'Spoke' site. The 'Hub' site will be responsible for organising and conducting all study visits, (apart from the study

intervention as detailed above), collecting all study data, communicating with trial participants and liaising with the site/trust carrying out the study intervention as required.

By the nature of the different delivery of treatments and the need to record treatment-specific operative parameters and resource use, blinding of the participant, surgeon, clinical team, Health Economics and TMG is not possible.

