7.1.2. Consent

Potentially eligible participants will be invited for a research specific screening visit where informed consent will be taken. Potential participants will have sufficient time to review the trial documentation prior to this screening visit this will likely be 24 hours but may be less depending on patient driven requests and circumstances, e.g. the patient living a distance away from the hospital and not wishing to return for a separate visit to consent to the study. Patients will be encouraged to ask questions about the trial and consider whether they wish to participate. Patients should be willing to have at least two of the four possible procedures.

The patient will be informed of their right to withdraw from the trial at any time without being subject to any resulting detriment, by revoking his informed consent. Consent discussions will be documented in the participant's medical records.

Written informed consent for the trial will be taken by a delegated member of the research team, (in agreement with local site policies) who is appropriately trained and delegated to do so. All consenting staff will be required to complete the study specific training which will include a section on trial consent and the importance of delivering information about the various study arms with equipoise, in order to avoid inadvertently biasing potential patients. Consent will be obtained prior to any activities undertaken as part of the screening visit (Visit 1).

The original signed consent form will be retained in the Investigator Site File (ISF), with a copy provided to the patient and a copy filed or scanned into the patient's medical notes (depending on local hospital records/patient notes). Participants will specifically consent to their GP and care team (and referring PIC where applicable), being informed of their participation in the trial and for long term follow up by notes review.

In the case of protocol amendments or information becoming available which may affect the participant's willingness to continue in the trial, it may be necessary to re-consent the participant on an updated consent form (after necessary approvals are obtained).

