7.2. Randomisation

7.2.1. Randomisation scheme

There will be 11 randomisation schemes available (six 1:1 options, four 1:1:1 options and one 1:1:1:1 option:

- 1. Prostatic urethral lift (PUL) vs Rezum vs Temporary Implantable Nitinol Device (iTIND) vs TURP
- 2. TURP vs Rezum vs PUL
- 3. TURP vs PUL vs iTIND
- 4. TURP vs Rezum vs iTIND
- 5. PUL vs iTIND vs Rezum
- 6. TURP vs Rezum
- 7. TURP vs PUL
- 8. TURP vs iTIND
- 9. Rezum vs PUL
- 10. Rezum vs iTIND
- 11. PUL vs iTIND

For each scheme, randomisation will be performed using permuted random blocks of variable length.

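### The primary estimand names one population of eligible men for all three comparisons, but each MIT–TURP effect is estimated only in men willing to be randomised to both procedures

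*Protocol*

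**What the plan says.** Protocol 10.3.1 sets out the main primary estimand in a table. Its population row reads "Patients offered surgery for BOO and meeting the PREMISE eligibility" criteria. There is one such row for PUL, Rezum and iTIND together, and it carries no condition on which procedures a man would accept. The five inclusion criteria in 6.1 carry no such condition either.

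Willingness enters elsewhere. Section 4 states: "Patients who are willing to receive at least two of the four trial interventions can be randomised among treatments they are willing to receive". Section 7.1.2 adds: "Patients should be willing to have at least two of the four possible procedures". Section 7.2.1 then lists 11 schemes ("six 1:1 options, four 1:1:1 options and one 1:1:1:1 option").

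The analysis set for each test follows from the schemes. Section 10.2 says "To test each hypothesis, participants will be pooled across the following randomisation schemes" and tabulates four schemes per comparison, each containing TURP and the MIT concerned. Section 10.3.1 repeats the rule: "For the pairwise comparison of each MIT to TURP data will be pooled across randomisation schemes as shown in Section 10.2". Section 10.2 also acknowledges that "not all participants will contribute to each analysis", but draws only the consequence that more men may have to be recruited.

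The main model in 10.3.1 has randomisation scheme as a fixed effect. Pooling over all 11 schemes, with weighting or a similar method, is a supplementary analysis.

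**The concern.** An estimand's population should be the one whose effect the main analysis estimates. Here the stated population is every eligible man offered surgery, and the men analysed are those who accept both TURP and the given MIT. If the effect of an MIT relative to TURP depends on what a man is prepared to accept, the two can differ.

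The group left out matters clinically. The Rationale, describing PUL, says: "PUL is intended for men with bothersome LUTS, where intervention is being considered, but TURP or equivalent is not", and the sentence goes on to say that it is the patient who finds TURP unacceptable. A man who declines TURP cannot be in the PUL–TURP comparison. The passage is device background and does not define the trial's claim, but it shows that the omitted men are not a marginal category in the protocol's own account.

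At stake is the wording of the conclusion. Guideline bodies are named as intended users of the results. They would read non-inferiority as applying to all men eligible for surgery. Seeing three results under one population row, they could also take them as referring to the same men.

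**Working it through.** **1. The plan's sample size, for reference.** Inputs from 10.2: margin 3, SD 6.3, true difference 0, one-sided alpha 0.0195, power 90%.

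- Normal formula: n = 2 × (2.064 + 1.282)² × 6.3² / 3² ≈ 98.7, so 99 per arm. The t-based version needs 100 (power 0.9006), as stated.
- Attrition of 25%: 100 / 0.75 = 133.3, so 134; 4 × 134 = 536, as stated.

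These figures are set per intervention for each comparison, and they do not depend on how the population is worded.

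**2. Which schemes feed which test** (numbering of 7.2.1, pooling table of 10.2):

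- PUL vs TURP: schemes 1, 2, 3, 7
- Rezum vs TURP: schemes 1, 2, 4, 6
- iTIND vs TURP: schemes 1, 3, 4, 8
- In no main comparison: schemes 5, 9, 10, 11 (no TURP)

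Any two comparisons share two schemes. Only scheme 1 is in all three. Men who would accept only one procedure satisfy the stated population unless inclusion criterion 4 (willingness to comply with trial procedures) is read to exclude them, and they cannot be randomised at all.

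**3. Overlap of the TURP groups.** The protocol gives no uptake by scheme, so equal uptake is assumed here for illustration only. The TURP fraction is 1/4 in the four-way scheme, 1/3 in each three-way scheme and 1/2 in a two-way scheme.

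- TURP controls per comparison, in units of one scheme's size: 1/4 + 1/3 + 1/3 + 1/2 = 17/12
- Shared by two comparisons: (1/4 + 1/3) / (17/12) = 7/17 = 41%
- Common to all three: (1/4) / (17/12) = 3/17 = 18%

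Unequal uptake would move these shares. The groups are neither identical nor disjoint.

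**4. Stated population against estimated population.** Let w be the share of eligible men willing to accept both procedures, D_in the true MIT–TURP difference in them, and D_out the difference in the rest. Then

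D_all = w × D_in + (1 − w) × D_out, so D_all − D_in = (1 − w) × (D_out − D_in).

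The main analysis estimates D_in; the table names D_all. The protocol gives neither w nor D_out, so neither the size nor the sign of the gap can be computed. As a scale, if D_in = 0, D_all reaches the margin of 3 when D_out = 3 / (1 − w):

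- w = 0.3: 4.3 points
- w = 0.5: 6.0 points
- w = 0.7: 10.0 points

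If the MIT does relatively better in the other men, D_all lies on the favourable side of D_in.

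**5. Whether another part of the plan closes the gap.** The scheme fixed effect adjusts mean outcome between schemes; it does not carry a treatment effect over to men who were not compared. Scheme is not in the subgroup list of 10.3.4. The 11-scheme analysis brings in randomised men who decline TURP, but it is supplementary, it leaves the primary estimand unchanged, and it compares these men with TURP by weighting and not by randomisation. Criterion 4 could at most imply a general willingness and cannot produce three comparison-specific populations.

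**The case against.** The restriction is unavoidable and openly disclosed. A man who refuses TURP cannot be randomised to it under any design, and sections 4, 7.1.2, 7.2.1 and 10.2 all say that men are randomised only among treatments they accept. The pooling rule stands in the same section as the estimand table, so a careful reader can see who is compared. The supplementary analysis already reaches the men in schemes 5, 9, 10 and 11. Baseline tables and a scheme interaction are commonly left to the SAP.

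Much of this stands. The design is not at fault, and missing reporting detail is no finding. But the protocol itself states the population attribute, and states it more widely than its main analysis supports. Disclosure in other sections does not correct that row.

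Three stronger readings are tempting, and the documents do not support them.

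- *The stated population goes untested, or the estimates are biased.* Each comparison is made in a subset of the stated population, randomised within scheme and adjusted for scheme. Nothing is biased within a comparison.
- *The type I error is inflated.* The population mismatch does not alter the level of the 0.0195 test for the men compared. An error rate for the wider population would need an assumed share and an assumed effect difference, with an assumed sign.
- *The plan ranks the MITs through a common TURP group.* Section 10.2 states three separate pairwise hypotheses. Section 10.3.1 compares the experimental arms with one another and admits that this is not powered. No indirect ranking is planned.

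**Conclusion.** The point holds as a mismatch between the target population and the data. The estimand table gives one population of all eligible men. The main analysis estimates three effects, each in eligible men willing to be randomised between TURP and one MIT, with partly overlapping but different TURP groups. Men who decline TURP are in none of the three.

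This conclusion rests only on the text of 6.1, 7.2.1, 10.2 and 10.3.1. The overlap shares of 41% and 18% rest on assumed equal uptake, and the break-even values of 4.3 to 10.0 points on assumed values of w with no difference in willing men; both are illustrations. The effect on the answer for the stated population cannot be sized or signed from the protocol. The internal validity of each comparison and the sample size are unaffected. What changes is the population for which non-inferiority may be claimed.

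**What to change.** In the estimand table of 10.3.1, define the population separately for each comparison: eligible men willing to be randomised to both TURP and that MIT. Bring the primary objective into line, and word each non-inferiority conclusion to that population. Add one sentence saying that the three MIT–TURP differences refer to different populations and are not directly comparable.

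Optionally, add an exploratory treatment-by-scheme estimate for each comparison, using the scheme variable already recorded. The trial is not powered for it, so it should be described as exploratory.

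The cost is a few lines of protocol and SAP wording. No recruitment target, test or significance threshold changes. The downside is a narrower headline: the trial would speak for men open to both procedures, not for every man offered surgery.

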10.3.4. Subgroup Analyses

For the primary outcome we will explore subgroup effects through inclusion of an interaction parameter in the primary analysis model. Variables we will consider are:

- Age
- Prostate size
- Symptoms based on I-PSS
- Flow rate
- Voiding efficiency

Full details of all analyses will be pre-specified in the statistical analysis plan.

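### The main I-PSS model uses baseline I-PSS as its only patient-level baseline measure; adding age, prostate volume and the adherence covariates would give modest precision and some robustness at almost no cost

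*Protocol*

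**What the plan says.** Protocol section 10.3.1 makes the per-protocol population the main analysis set for the 12-month I-PSS comparison of each minimally invasive treatment with TURP. The outcome model is a mixed model for the six- and twelve-month scores, "with fixed effects for baseline I-PSS, randomisation scheme, and a treatment-by-time interaction term", with random effects for site and for individual within site.

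If more than 5% of eligible men in either arm of a comparison do not undergo their allocated treatment, the same section adds inverse probability weights. These come from a logistic model of adherence fitted separately in each arm, with "prespecified baseline measures as covariates". The covariates are not named; they are to be agreed before data lock. They are used to build the weights, and nothing in the section carries them into the outcome model. The sensitivity analysis for the weighting is an unweighted repeat. Intention-to-treat, modified intention-to-treat, as-treated and complier-average analyses are supplementary.

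Section 10.3.4 lists five baseline variables for exploratory interaction tests, among them age and "Prostate size". Section 10.2 takes no numerical credit for covariate adjustment; it remarks only that adjusting for baseline I-PSS should lift power above 90%.

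**The concern.** A per-protocol estimate excludes men after randomisation. The trial is open-label, section 7.4 expects waiting times to differ by intervention, and section 7.13.2 lets men decline their allocation and stay in follow-up. Adherence could therefore be selective and could differ by arm.

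When weighting is used, the correction for that selection on the adherence covariates runs through the weight model alone. That model is fitted per arm and may have few non-adherers to work with. Putting the same covariates in the outcome model as well usually recovers precision and gives a second route to removing imbalance if the weights are poor. The planned unweighted repeat shows how much the weights matter, but it does not protect against a wrong weight model.

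What is at stake is some width in the confidence interval set against a 3-point margin, and some robustness of the main estimate.

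**Working it through.** **Inputs from Protocol section 10.2.** Margin: "A non-inferiority margin of three points is used". SD 6.3. True difference zero: "Assuming a minimally invasive arm has the same mean I-PSS as TURP". One-sided alpha 0.0195, power 90%. Stated requirement: "we would require 12-month information on 100 participants per intervention for each comparison for 90% power to conclude non-inferiority". Attrition 25%, giving 134 per arm.

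**1. Reproduce the plan's figure.**
- n per arm = 2 × (6.3/3)² × (2.064 + 1.282)² = 8.82 × 11.19 = 98.7, so 99 by the normal approximation. The noncentral t version gives 100 (power 90.06%).
- 100/0.75 = 133.3, so 134; 4 × 134 = 536.
- The stated figures hold.

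**2. Precision from extra covariates.** If they explain a further fraction R² of outcome variance, the SD becomes 6.3 × √(1 − R²). At 100 per arm:
- SE = 6.3 × √(0.02 × (1 − R²))
- power = Φ(3/SE − 2.064)
- 95% half-width = 1.96 × SE

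With no extra covariates, SE = 0.891, 3/0.891 = 3.367, and power = Φ(1.303) = 90.4%. R² is an assumption, so a range is shown.

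| Extra R² | SD | 95% half-width | Power |
|---|---|---|---|
| 0% | 6.30 | 1.75 | 90.4% |
| 2% | 6.24 | 1.73 | 90.9% |
| 5% | 6.14 | 1.70 | 91.8% |
| 10% | 5.98 | 1.66 | 93.1% |
| 20% | 5.63 | 1.56 | 95.6% |

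The interval narrows by about 1% at R² = 2%, 5% at 10% and 11% at 20%. If baseline I-PSS already explains 10% (also assumed), power starts at 93.1%, and a further 2% to 10% takes it to between 93.6% and 95.6%. The gain is of similar size.

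**3. Data behind the weight model.** At the trigger, 5% of 134 is 6.7 non-adherers in an arm. A logistic model with several covariates is fragile at that number: simulation met separation warnings, and one setting with low non-adherence gave no usable weighted estimate.

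**4. Weighted model with and without the covariate (simulation).** Settings: 134 per arm, 25% missing at random, 2,000 replicates, and a covariate with R² = 10%. Non-adherence was assumed to be 10% in one arm and 20% in the other, with selection in opposite directions, which is a deliberately adverse case. The outcome model was linear and correctly specified.
- Weight model correct: bias is about zero either way. The empirical SE falls from 0.96 to 0.91, about 10% less variance, since (0.91/0.96)² = 0.90.
- Weight model wrong: bias is −0.56 I-PSS points without the covariate and −0.03 with it.

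The SEs are plausible by hand. Evaluable adherers number 134 × 0.75 × 0.9 = 90.5 and 134 × 0.75 × 0.8 = 80.4. Ignoring variance added by the weights, SE = 6.3 × √(1/90.5 + 1/80.4) = 0.97, and multiplying by √0.9 gives 0.92.

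A separate simulation of 600 trials assumed non-adherence of 20% and 8%, five covariates and R² = 9%. The SD of the estimate fell from 0.987 to 0.925, a variance ratio of 0.88. Both simulations used a simple weighted linear model, not the planned repeated-measures model with site effects.

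**The case against.** The strongest reply is that nothing here is wrong. Adjusting for the baseline outcome, scheme and site, with weights for non-adherence, is a coherent plan, and further covariates are a refinement. That stands, and it sets the weight of the point. Several stronger readings are tempting, and the protocol does not support them.

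- **That covariates judged important are left out.** The adherence covariates are unnamed. Baseline I-PSS, already a fixed effect, may be one of them, and the statistical analysis plan, not available here, may name the rest. They are chosen to predict adherence and help precision only if they also predict 12-month I-PSS. The list in section 10.3.4 is exploratory and does not declare its variables prognostic.
- **That the estimate is unprotected when the 5% trigger is not met.** Non-adherence is then at most 5% in each arm, which limits selection. Baseline I-PSS, scheme and site remain in the model, and the supplementary analyses are still run.
- **That adding the covariates makes the estimate right if either model is right.** This needs an adequate outcome model. The change adds main effects only, and section 10.3.4 treats some of these variables as possible effect modifiers. If they do modify the effect, a poor weight model would not be fully rescued. The fall in bias from 0.56 to 0.03 comes from an adverse case with a correct outcome model and is not a forecast.
- **That the same set is needed in the secondary questionnaire models.** The protocol gives no basis for that.

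It is also true that flow measures, if chosen, may lack valid values, because section 7.5.4 lets men enrol who cannot void more than 125 ml. The change should be limited to covariates with complete baseline data.

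**Conclusion.** The point holds as an inexpensive improvement, not as an error or a contradiction. As written, the adherence covariates reach the main estimate only through conditional weights, and age and prostate volume, though collected at entry, are not in the outcome model. The omission does not bias a correctly weighted analysis, does not raise its type I error and does not undermine the 100, 134 or 536, which take no credit for covariates.

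The precision forgone is about 1% to 5% of the interval width, or 0.5 to 2.7 percentage points of power, for an assumed extra R² of 2% to 10%. The robustness forgone could be larger, about half a point against a margin of 3 in the adverse case simulated. That figure depends on assumed selection, assumed prognostic strength and a correct linear outcome model, none of which the protocol quantifies.

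**What to change.** In Protocol section 10.3.1, before any unblinded data are seen, state that age, prostate volume and the prespecified adherence-model covariates with complete baseline data are fixed effects in the main I-PSS model for all three comparisons with TURP, whether or not weighting is triggered. Name the covariates in that text, because no adherence model is fitted below the trigger and the list must exist without one. Keep the currently stated model as a sensitivity analysis. If the trial statisticians have already seen unblinded outcome data, section 10 provides for approval by the blinded methodology advisor.

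The cost is a sentence or two of text and a few degrees of freedom. No new data are needed for age, which follows from date of birth, or for prostate volume, which is required for eligibility.
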